## **8.5      **Unscheduled Visit (if needed)****

An Unscheduled Visit may occur at any time during this trial. Any of the following activities may be performed:

- Interim medical history, including an assessment for new medical conditions, stability of chronic diseases and symptoms suggestive of AESIs (including Protocol Specified AESIs, MAAEs, NOCMCs and PIMMCs) will be obtained by interview of subjects and any changes since the previous clinic visit or phone call will be noted (if indicated).
- All concomitant medications will be recorded on the appropriate DCF (if within 28 days after first study vaccination). Receipt of any non-study influenza vaccines will also be recorded on the appropriate DCF (if within 365 days after first study vaccination).
- All AE/SAEs will be recorded on the appropriate DCF. Unsolicited AEs (if occurs within 28 days of the first study vaccination). SAEs and AESIs (including Protocol Specified AESIs, MAAEs, NOCMCs and PIMMCs) that have occurred since the previous clinic visit will be solicited (if within 365 days after first study vaccination).

- Memory Aid information will be reviewed with subjects (if within 7 days after the first study vaccination).
- Vital signs, including oral temperature, pulse and BP, may be obtained if indicated. Subjects must not eat or drink anything hot or cold, or smoke within 10 minutes prior to taking oral temperature.
- A targeted physical examination, including an assessment for signs suggestive of AESIs (including Protocol Specified AESIs, MAAEs, NOCMCs and PIMMCs), may be performed, if indicated based on review of interim medical history, by a study clinician licensed to make medical diagnoses and listed on the Form FDA 1572 as the site PI or sub-investigator.
- The study vaccination site will be examined (if within 7 days after study vaccination).
- Post administration reactogenicity assessment will be performed (if within 7 days after the first study vaccination).
- Site investigators have the discretion of administering 2019/2020 Fluzone or Flublok QIV earlier than the Day 90 window (i.e. earlier than Day 76) if 10% or more of surveillance samples in the CDC geographic region surrounding the local site test positive for influenza.
- Approximately 6 mL of venous blood will be collected for clinical safety labs (WBC, Hgb, PLT, ALT, T. Bili, AST, GGT, ALP serum lipase and amylase and Cr) to be performed by the Central Clinical Laboratory (if indicated).
- Approximately 20 mL of venous blood will be collected for serological assays.

## **9 ASSESSMENT OF SAFETY**

### **9.1 Specification of Safety Parameters**

Safety will be assessed by the frequency and severity of:

1. SAEs occurring from the time of the first study vaccination through approximately 12 months after the first study vaccination.
2. Solicited AEs – reactogenicity events occurring from the time of the first study vaccination through 7 days after the first study vaccination:
  - a) Injection site reactions including pruritus, ecchymosis, erythema, induration, edema, pain, and tenderness.
  - b) Systemic reactions including fever, feverishness, fatigue, malaise, myalgia, arthralgia, headache, and nausea.
3. Clinical safety laboratory AEs occurring from the time of the first study vaccination through approximately 7 days after the first study vaccination. Parameters to be evaluated include WBC, Hgb, PLT, ALT, T. Bili, AST, GGT, ALP, serum lipase, serum amylase, and Cr.
4. Unsolicited AEs –non-serious AEs occurring from the time of the first study vaccination through approximately Day 29.
5. AESIs (including Protocol Specified AESIs, MAAEs, NOCMCs and PIMMCs) occurring from the time of the study vaccination through approximately 12 months after the first study vaccination.

### **9.2 Methods and Timing for Assessing, Recording and Analyzing Safety Parameters**

#### **9.2.1 Adverse Events**

**Adverse Event (AE):** ICH E6 GCP defines an AE as any untoward medical occurrence in a patient or clinical investigation subject administered a pharmaceutical product regardless of its causal relationship to the study treatment. The FDA defines an AE as any untoward medical occurrence associated with the use of a drug in humans, whether or not considered drug related.

An AE can therefore be any unfavorable and unintended sign (including an abnormal laboratory finding), symptom or disease temporally associated with the use of a medicinal (investigational) product. The occurrence of an AE may come to the attention of study personnel during study visits and interviews of a study recipient presenting for medical care, or upon review by a study monitor.

AEs, including solicited injection site and systemic (subjective and quantitative) reactions, not meeting the protocol-defined criteria for SAEs, will be recorded on the appropriate DCF and entered into the eCRF. Information to be collected for unsolicited non-serious AEs includes event description, date of onset, licensed study physician's assessment of severity and relationship to study product or alternate etiology (if not related to study product) (assessed only by those with the training and authority to make a diagnosis and listed on the Form FDA 1572 as the site PI or sub-investigator), date of resolution, seriousness, and outcome. AEs occurring during the trial-collection and reporting period will be documented appropriately regardless of relationship to study product. AEs will be followed through resolution.

Any medical condition that is present at the time that the subject is screened will be considered as baseline and not reported as an AE. However, if the severity of any pre-existing medical condition increases, it will be recorded as an AE.

AEs must be assessed for severity and relationship to study product (see definitions below). AEs characterized as intermittent require documentation of onset and duration of each episode. The start and stop date of each reported AE will be recorded on the appropriate DCF and entered into the eCRF.

**Adverse Events of Special Interest (AESI):** An adverse event of special interest (serious or nonserious) is one of scientific and medical concern specific to the sponsor's product or program, for which ongoing monitoring and rapid communication by the investigator to the sponsor can be appropriate. Such an event might warrant further investigation in order to characterize and understand it. Depending on the nature of the event, rapid communication by the trial sponsor to other parties (e.g., regulators) might also be warranted.

**Medically-Attended Adverse Events (MAAEs):** For each unsolicited AE experienced, the subject will be asked if he/she had received medical attention, defined as hospitalization, an emergency room visit or an otherwise unscheduled visit to or from medical personnel for any reason. AEs characterized by such unscheduled medical care will be designated as MAAEs.

**New-Onset Chronic Medical Conditions (NOCMCs):** NOCMCs are defined as any new ICD-10 diagnosis (10th revision of the International Statistical Classification of Diseases and Related Health Problems) that is applied to the subject during the course of the study, after receipt of the study agent, that is expected to continue for at least 3 months and requires continued health care intervention.

**Potentially Immune-Mediated Medical Conditions (PIMMCs):** PIMMCs constitute a group of AEs that includes diseases which are clearly autoimmune in etiology and other inflammatory and/or neurologic disorders which may or may not have autoimmune etiologies. PIMMCs currently in effect are presented in [Appendix B: Adverse Events of Special Interest](#).

**Protocol Specified AESIs:** Dry Eye, Dry Mouth and Tearing

**Severity of Event:** AEs will be assessed by a licensed study physician listed on the Form FDA 1572 as the site PI or sub-investigator using a protocol-defined grading system (see [Sections 9.2.2](#) and [9.2.3](#)). For events not included in the protocol-defined grading system, the following guidelines will be used to quantify severity:

- Mild (Grade 1): Events require minimal or no treatment and do not interfere with the subject's daily activities.
- Moderate (Grade 2): Events result in a low level of inconvenience or concern with therapeutic measures. Moderate events may cause some interference with functioning and daily activities.
- Severe (Grade 3): Events interrupt the subject's daily activities and may require systemic drug therapy or other treatment. Severe events are usually incapacitating.

**Relationship to Study Product:** The licensed study physician's assessment of an AE's relationship to study product is part of the documentation process, but it is not a factor in determining what is or is not reported in this trial. If there is any doubt as to whether a clinical observation is an AE, the event should be reported. The relationship to study product must be assessed for AEs using the terms: related or not related. In a clinical trial, the study product must always be suspect. To help assess, the following guidelines are used:

- Related – There is a reasonable possibility that the study product caused the AE. Reasonable possibility means that there is evidence to suggest a causal relationship between the study product and the AE.

- Not Related – There is not a reasonable possibility that the administration of the study product caused the event.

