
 
• To assess protocol specified AESIs, medically-attended adverse events (MAAEs), including new-onset chronic medical conditions (NOCMCs) and potentially immune-mediated medical conditions (PIMMCs) that occur after receipt of study product.
 
	
 
• Occurrence of all protocol specified AESIs, MAAEs, including NOCMCs and PIMMCs, from the time of the first study vaccination through approximately 12 months following the first vaccination.
 

Secondary Immunogenicity Objectives
	
Secondary Immunogenicity Outcome Measures

 
• To assess the HAI, Neut and NAI ELLA responses to the 2019/2020 QIV strains prior to (Day 1) and approximately 28 days after vaccination with the 2019/2020 QIV in all study groups
 
	
 
• The percentage of subjects achieving an HAI titer <math>\geq 1:40</math> against 2019/2020 QIV strains approximately on Days D90 (baseline) and D118 (28 days post-2019/2020 vaccine) for each study group.
 
• The percentages of subjects achieving HAI, Neut and NAI titer seroconversion, against 2019/2020 QIV strains on
 

	
approximately Day 118 for each study group (NAI titers will only be assessed on study groups 1,2 and 3).
 
 
• Serum Neut, HAI and NAI GMTs against 2019/2020 QIV strains approximately on Days D90 (baseline) and D118 (28 days post-2019/2020 QIV) for each study group (NAI titers will only be assessed on study groups 1,2 and 3).
 
• Ratio of serum Neut, HAI and NAI GMTs against 2019/2020 QIV strains between adjuvanted and unadjuvanted study groups approximately on Days D90 (baseline) and D118 (28 days post-2019/2020 QIV). NAI titers will only be assessed on study groups 1,2 and 3.
 
• Serum Neut, HAI and NAI GMFRs against 2019/2020 QIV strains from baseline (D90) on approximately D118 for each study group (NAI titers will only be assessed on study groups 1,2 and 3).
 

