## **6.5 Concomitant Medications/Treatments**

Administration of any medications, therapies or vaccines will be recorded on the appropriate DCF. Concomitant medications will include all current medications and medications taken in the 60 days prior to signing the ICF through approximately Day 29 after first study vaccination or early termination, whichever occurs first. Receipt of any influenza vaccine during the 2018/2019 influenza vaccine season prior to receipt of the study vaccine (regardless of the date of receipt) will be documented. Medications reported in the electronic case report form (eCRF) are limited to those taken within 30 days prior to the first study vaccination through approximately 28 days after the first study vaccination. Prescription and over-the-counter drugs will be included as well as herbals, vitamins and supplements.

In addition, receipt of any non-study influenza vaccines will be solicited through approximately 365 days after the first study vaccination and reported in the eCRF. Use of a new medication should prompt evaluation for the occurrence of any MAAE, including a new diagnosis of chronic medical disease or condition.

Medications that might interfere with the evaluation of the investigational product(s) should not be used during the trial-reporting period (approximately 12 months after the first study vaccination) unless clinically indicated as part of the subject's health care. Medications in this category include the prohibited medications per the Subject Exclusion Criteria (see [Section 5.1.2](#)). In addition, the site PI or appropriate sub-investigator may identify other medications that should not be used due to a risk to subject safety or assessment of reactogenicity and immunogenicity.

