### **8.2.1 Visit 02, Day 2, Clinic Visit**

**(Window: Day 2 +1 day post study vaccination)**

- Interim medical history, including an assessment for new medical conditions, stability of chronic diseases and symptoms suggestive of AESIs (including Protocol Specified AESIs, MAAEs, NOCMCs and PIMMCs), will be obtained by interview of subjects and any changes since the previous clinic visit will be noted.

- All concomitant medications (including solicitation for receipt of any non-study influenza vaccines) will be recorded on the appropriate DCF.
- All AE/SAEs will be recorded on the appropriate DCF.
- Memory Aid information will be reviewed with subjects.
- A targeted physical examination, including an assessment for signs suggestive of AESIs (including Protocol Specified AESIs, MAAEs, NOCMCs and PIMMCs), may be performed, if indicated based on review of interim medical history, by a study clinician licensed to make medical diagnoses and listed on the Form FDA 1572 as the site PI or sub-investigator.
- The study vaccination site will be examined.
- Approximately 3 mL of venous blood will be collected for transcriptomic assays.
- Counsel on avoidance of pregnancy.

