### 9.2.2 Reactogenicity

Reactogenicity events are AEs that are common and known to occur following administration of this type of study vaccine. The following Toxicity Grading Scales will be used to grade solicited injection site and systemic (subjective and quantitative) reactions:

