**Table 4: Injection Site Reactogenicity Grading**

Injection Site Reaction	Mild (Grade 1)	Moderate (Grade 2)	Severe (Grade 3)
Pain – experienced without touching the injection site (spontaneous discomfort)	Subject is aware of pain, but it does not interfere with daily activity, and if pain medication is used, it is Over the Counter (OTC) and used for less than 24 hours	Subject is aware of pain; there is interference with daily activity or OTC pain medication is used for more than 24 hours	Subject is aware of pain, and it prevents daily activity or pain requires prescription medication
Tenderness-experienced with touching the injection site	Subject is aware of pain, but it does not interfere with daily activity, and if pain medication is used, it is Over the Counter (OTC) and used for less than 24 hours	Subject is aware of pain; there is interference with daily activity or OTC pain medication is used for more than 24 hours	Subject is aware of pain, and it prevents daily activity or pain requires prescription medication
Pruritus	Does not interfere with daily activity	Interferes with daily activity	Prevents daily activity or requires prescription medication
Ecchymosis (Bruising)*	Does not interfere with daily activity	Interferes with daily activity	Prevents daily activity
Erythema (Redness)*	Does not interfere with daily activity	Interferes with daily activity	Prevents daily activity
Induration (Hardness)/Edema (Swelling)*	Does not interfere with daily activity	Interferes with daily activity	Prevents daily activity

\* Will also be measured in mm but size will not be used as halting criteria.

Ecchymosis, erythema and induration/edema as analyzed by measurement will be graded as follows:

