16.2.7 Adverse Events

Listing 20: 16.2.7.1: Solicited Events – Systemic Symptoms

Subject ID	Study Arm	Post Dose Day	Assessment ^a	Symptom	Severity	Attributed to Alternate Etiology? ^b	Alternate Etiology
			MA				
			Clinic				

^a MA = Data reported by subject on the Memory Aid and reviewed by clinic staff and reported in Solicited Events eCRF.

^b Grade 3 events only.

Clinic = Data collected by clinic staff during physical exam or symptom assessment (treatment administration record, in-clinic assessment, etc.)

Listing 21: 16.2.7.2: Solicited Events – Local Symptoms

Subject ID	Study Arm	Post Dose Day	Assessment ^a	Symptom	Severity
			MA		
			Clinic		

^a MA = Data reported by subject on the Memory Aid and reviewed by clinic staff and reported in Solicited Events eCRF.

Clinic = Data collected by clinic staff during physical exam or symptom assessment (treatment administration record, in-clinic assessment, etc.)

Listing 22: 16.2.7.3: Unsolicited Adverse Events

Adverse Event	Associated with Dose No.	No. of Days Post Associated Dose (Duration)	Severity	MAAE?	Relationship to Study Vaccination	In Not Related, Alternative Etiology	Action Taken with Study Vaccination	Subject Discontinued Due to AE	Outcome	MedDRA System Organ Class	MedDRA Preferred Term
Study Arm: , Subject ID: , AE Number:											
Comments:											
Study Arm: , Subject ID: , AE Number:											
Comments:											
Note: For additional details about SAEs, see Table: xx.											

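### The medical-attention question is put only for unsolicited AEs, so an unscheduled visit for a solicited reaction has no explicit prompt and no MAAE flag in the solicited listings

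*Protocol*

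**What the plan says.** - **Outcome.** Protocol Table 1, repeated in SAP 3.1, sets the secondary safety measure as "Occurrence of all protocol specified AESIs, MAAEs, including NOCMCs and PIMMCs, from the time of the first study vaccination", running to about 12 months.
- **Ascertainment.** Protocol 9.2.1 defines an MAAE through a question: "For each unsolicited AE experienced, the subject will be asked if he/she had received medical attention". Medical attention means hospitalization, an emergency-room visit or another unscheduled visit. The next sentence reads "AEs characterized by such unscheduled medical care will be designated as MAAEs". SAP 3.2 does not define MAAE.
- **Solicited reactions.** Protocol 9.2.2 states that "Reactogenicity events are AEs that are common and known to occur following administration of this type of study vaccine". They are collected from the first vaccination through 7 days after it (Protocol 9.1).
- **Other routes to an MAAE.** The Day 2 visit includes an interim history in which "symptoms suggestive of AESIs (including Protocol Specified AESIs, MAAEs, NOCMCs and PIMMCs), will be obtained by interview of subjects"; the Day 8 visit has the same wording. Protocol 6.5 adds: "Use of a new medication should prompt evaluation for the occurrence of any MAAE".
- **SAP displays.** "Listing 22: 16.2.7.3: Unsolicited Adverse Events" carries an MAAE column, and so does the AESI listing (Table 135). Listings 20 and 21, for solicited systemic and local symptoms, do not. Table 117 has a row for subjects with at least one MAAE, by arm, without stating which events feed it.

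**The concern.** The outcome is meant to include all MAAEs, but the only stated question about medical attention goes to part of the AEs. Take a severe headache on Day 2 that sends a subject to an emergency room, without admission. It is a solicited event. Followed literally, 9.2.1 does not ask whether it was medically attended, and the solicited listing cannot show that it was.

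The gap falls in the week when vaccine reactions occur. Protocol 2.3.1 reports more local and systemic reactions with AF03, and more local reactions with the earlier Advax-CpG246.1 formulation. Any missed events could therefore be more frequent in adjuvanted arms, making the by-arm MAAE row look more alike than it should. Sites could also settle the question differently, while SAP 6.7 pools all sites on the ground that AE assessment is standardized.

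**Working it through.** There is no stated figure to reproduce. The check is of wording and data flow, with one illustration of scale.

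**1. Who is asked.** The question in 9.2.1 is limited to unsolicited AEs. No section of either document puts it to subjects for a solicited reaction. The Memory Aid contents in Protocol 8.1.2 are temperature, solicited reactions, unsolicited AEs and medications; medical attention is not among them.

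**2. What is designated.** The designation sentence speaks of AEs generally, and solicited reactions are AEs. So the rule does not exclude a medically attended solicited reaction. It leaves it unasked.

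**3. Where it could be recorded.** Table 135 calls for relationship, action taken, outcome and MedDRA terms. Listings 20 and 21 show none of these; Listing 20 adds only alternate etiology, for grade 3 events. As displayed, a solicited record could reach Table 135 only if it were entered again as an unsolicited AE or AESI, and neither document gives a rule for that.

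**4. What the safeguards reach.** The interviews mention MAAEs but do not tell the site to ask about unscheduled care for a solicited reaction. The new-medication prompt does reach many relevant cases: grade 3 pruritus, for example, is "Prevents daily activity or requires prescription medication", and Table 4 (pain, tenderness) and Table 6 (headache, nausea) have similar prescription clauses. It does not fire when a visit leads to no new medication. A reaction needing inpatient admission is an SAE in any case (Protocol 9.2.4), so the exposed set is emergency-room and other unscheduled visits without admission.

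**5. Scale, on assumed rates only.** Let p be the proportion of subjects with an unscheduled visit for a solicited reaction. The documents give no value; 0.5% to 5% is an assumption. Each arm has 40 subjects (Protocol 11.4.2), so four adjuvanted arms have 4 × 40 = 160. The expected number is n × p, and the chance of at least one is 1 − (1 − p)^n. As a check on the formula, p = 1% and n = 40 gives 1 − 0.99^40 = 33.1%, against 33 in Protocol Table 10.

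| Assumed p | Expected per arm of 40 | Chance of at least one in an arm | Expected among 160 |
|---|---|---|---|
| 0.5% | 0.2 | 18% | 0.8 |
| 1% | 0.4 | 33% | 1.6 |
| 2% | 0.8 | 55% | 3.2 |
| 5% | 2.0 | 87% | 8.0 |

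At each assumed rate these are ceilings on missed MAAEs, reached only if every other route fails.

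**The case against.** A reader might infer that medically attended solicited reactions are excluded from the MAAE count, and that MAAEs in adjuvanted arms are therefore undercounted. The documents do not support that. Nothing says such events are excluded, the designation sentence covers AEs in general, interviews at Days 2 and 8 seek MAAEs, and an emergency visit that ends in a new prescription should trigger the MAAE evaluation in 6.5. The Table 117 row is not restricted to unsolicited events. Listing shells are not the eCRF, which is not among the documents.

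The consequences are also limited. No MAAE hypothesis test is planned, and Protocol 11.6.2 expects few such events and reports them in listings. Solicited reactions are analysed directly by arm, severity and day, with exact intervals and logistic regression (SAP 9.3.1), and grade 3 solicited events feed the halting rules (Protocol 9.5). Protocol 2.3.1 says most AF03 reactions went within 3 days without medication and most Advax-CpG246.1 reactions resolved untreated within 1 or 2 days, which argues against frequent care-seeking.

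All of that stands against a claim of demonstrated undercounting. It does not remove the gap: none of these routes asks the question explicitly for a solicited reaction, and none gives it a flag in the solicited listings. Nor does 12-month MAAE collection show that capture is independent of the unsolicited-AE question. Protocol 9.1 stops non-serious unsolicited AEs at about Day 29, but SAP Table 124 tabulates unsolicited AEs through Day 365, so late MAAEs may still enter as unsolicited events.

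**Conclusion.** The point holds as a weakness in ascertainment. The stated rule, followed as written, seeks medical attention incompletely for an outcome meant to include all MAAEs, and the SAP solicited listings cannot show the status. Such events may be missed or treated differently across sites. That they are lost, or lost more often with adjuvant, is a plausible risk and not a finding: the direction rests on the reactogenicity reported in Protocol 2.3.1, and for Advax on CpG246.1, since CpG55.2 has not been given to humans before (Protocol 2.1).

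The size is unknown. The assumed rates above span 0.2 to 2.0 subjects per arm as a ceiling. What is affected is one descriptive secondary measure, over roughly the first 8 days of a 12-month window; primary safety outcomes and the reporting of the reactions themselves are untouched. This is a cheap improvement worth making. It would already be met if the eCRF or MOP collects the item, in which case only the protocol and SAP wording need to catch up.

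**What to change.** - In Protocol 9.2.1, extend the medical-attention question to every AE, solicited or unsolicited.
- Record a yes/no for solicited reactions at the Day 2 and Day 8 Memory Aid reviews, and in the follow-up phone call to subjects whose Day 8 visit falls on Day 7 (Protocol 8.2.2).
- Add an MAAE column to SAP Listings 20 and 21.
- Show the Table 117 MAAE row in total and split into solicited and unsolicited, so that the unsolicited-only count stays visible.

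If the intention is to leave solicited reactions out of the MAAE outcome, say so in 9.2.1 and SAP 3.2 and label the Table 117 row accordingly.

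The cost is one phrase in the protocol, one data field at contacts already planned, one column in two listings and a split row. The downside is slightly higher MAAE counts.
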